1.2 Schema, 4.1 Overall Design	The schema has been updated with respect to the removal of OCS	Schema has been updated as OCS information is no longer required.		
1.3 Schedule of Activities (SoA)	SoA has been updated for the removal of information regarding OCS and associated phases.	OCS requirement has been removed to align with the current management practice of SEA which does not include use of stable OCS use for prolonged periods of time and the changes are in line with prescribing information of the product.		
	Stringency of spirometry timings	To allow flexibility for the patients		
	(i.e. must be performed at the same time ±1 hour of the visit 1) has been removed.	by broadening the time window for the spirometry within the day of the study visit.		

Section # and Name	Description of Change	Brief Rationale			
	Advisory statement for 12-Lead ECG has been added.	To maintain the uniformity across the protocol.			
	Serum IgE (total) - Serum IgE has been removed from week 24 and IP discontinuation visit	Assessment of change from baseline is not an objective or endpoint of the study			
3.0 Objectives and Endpoints		Only a subset of patients (those completing or withdrawn from the study prior to protocol amendment 4) will be assessed for this endpoint where a structured OCS tapering schedule was mandated within the previous study protocols and protocol amendments			
	Description of estimands have been added for all primary, secondary and exploratory endpoints	The rationale to add estimands is that estimands provide the precise description of what is being estimated for primary endpoints also explain about how to deal with intercurrent events which may occur during the study.			
5 Study Population 6 Study Intervention 8 Efficacy Assessments	Inclusion criteria 5 has been updated with respect to the removal of requirement for background systemic corticosteroids. Information regarding OCS phases has also been removed.	OCS requirement has been removed to align with the current management practice of SEA which does not include the use of a stable OCS dose for prolonged periods of time and the changes are in line with prescribing information of the product. Only a subset of patients (those completing or withdrawn from the study prior to protocol amendment 4) will now be assessed for the			

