4.2. Scientific Rationale for Study Design

Though safety and efficacy of mepolizumab in patients with severe eosinophilic asthma has been established in various clinical studies across USA and Europe, this will be the first clinical study to assess safety in Indian patients.

Eosinophilic inflammation of the airways plays a central role in the pathogenesis of asthma (Seminario, 1994; Rothenberg, 1998; Wardlaw, 2000; Cohn, 2004). The overproduction of IL-5 has been specifically reported in patients with a variety of eosinophil associated disorders including asthma (Robinson, 1992; Sur, 1995). Mepolizumab binds with high specificity and affinity to human interleukin 5 (IL-5), the key cytokine responsible for regulation of blood and tissue eosinophils. A therapeutic strategy targeting IL-5 with mepolizumab represents a focused therapeutic option, which results in reduced eosinophil levels and important clinical benefits for patients with eosinophilic inflammation associated with severe asthma who are receiving optimised standard of care therapy.

There is significant unmet medical need to provide better treatment options in patients with severe eosinophilic asthma who need systemic corticosteroids for maintenance, given undesirable safety profile of OCS and the limited application of omalizumab in severe asthma (Normansell, 2014). In patients aged ≥12 years with severe eosinophilic asthma in the phase III studies, adding subcutaneous mepolizumab 100 mg q4w to current asthma therapy significantly reduced the rate of clinically relevant asthma exacerbations and significantly improved asthma control and had acceptable tolerability (with headache the most common adverse event). Further, the SIRIUS study demonstrated that in patients requiring daily oral glucocorticoid therapy to maintain asthma control, mepolizumab had a significant glucocorticoid-sparing effect. This study will also evaluate the OCS sparing effect in Indian patients with severe eosinophilic asthma (only to be assessed in patients who completed or withdrew from the study prior to the adoption of protocol amendment 4).

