3.3 EXPLORATORY OBJECTIVE

4. ESTIMANDS

Primary Endpoints:

Incidence of on-treatment adverse events (AEs), serious adverse events (SAEs) and adverse events of special interest (AESIs).

The primary estimand for this endpoint is described by the following attributes:

- Population: Severe refractory asthma patients in India with elevated eosinophils.
- Treatment condition: Participants to receive Mepolizumab 100mg SC every 4 weeks during 24 weeks treatment period.
- Variable/endpoint: Incidence of on-treatment adverse events (AEs), serious adverse events (SAEs) and adverse events of special interest (AESIs).
- Summary measure: Counts and percentages for incidence of at least one AE will be summarised overall, by system organ class and by preferred term.
- Key Intercurrent events & Strategy:
 - Discontinuation of treatment (for any reason) While on-treatment strategy will be used for treatment discontinuation. This will estimate the percentage of participants experiencing an AE, while receiving treatment. AEs will be defined as on-treatment between the first dose up to and including 28 days following the last dose of mepolizumab.

Supplementary Estimand:

This supplementary estimand will report all AEs regardless of the discontinuation of study treatment.

- Population: Severe refractory asthma patients in India with elevated eosinophils.
- Treatment condition: Participants to receive Mepolizumab 100mg SC every 4 weeks during 24 weeks treatment period.
- Variable/endpoint: Incidence of AEs and SAEs
- Key Intercurrent events & Strategy:

• Treatment discontinuation (for any reason) - Treatment policy strategy will be used for treatment discontinuation. This summary will therefore be inclusive of all on-treatment and post-treatment AEs.

Secondary Endpoints:

- Number of clinically significant exacerbations (including exacerbations requiring hospitalization or ED visits)
- Number of exacerbations requiring hospitalization or ED visits
- Number of exacerbations requiring hospitalization
- Change from baseline in clinic pre-bronchodilator FEV1 at week 24
- Change from baseline in clinic post bronchodilator FEV1 at week 24
- Change from baseline in ACQ-5 score at week 24
- Change from baseline in morning PEF during weeks 20 24

The estimand for the secondary endpoint are detailed here.

- Number of clinically significant exacerbations (including exacerbations requiring hospitalization or ED visits)

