At Visit 2 (Week 0), participants who meet the Treatment Period eligibility criteria will receive Mepolizumab 100mg SC every 4 weeks. Subsequently, participants will continue to receive with mepolizumab 100mg SC every 4 weeks. During this period, participants will remain on their baseline asthma medications. OCS use and OCS dose adjustment in participants will be as per the investigator's discretion and clinical practice.

5.1.4. Exacerbation Management during Treatment Period:

Anytime during the study when a participant experiences an exacerbation the exacerbation should be treated according to the investigator's clinical practice.

The participant will return for each subsequent Visit, to receive their subsequent doses of open label study treatment, as scheduled.

5.1.4. IP Discontinuation Visit:

The IP discontinuation visit will be performed 4 weeks following the last dose of mepolizumab with a window of ± 7 days. Also, if a participant permanently stops study intervention, the participant is not required to withdraw from the study. Every effort should be made by the PI/staff to keep the subject in the study to collect important efficacy and safety data. In the event of discontinuation of study, the end of study visit activities should be performed as specified in SoA table.

5.1.5. End of Study Visit:

A participant is considered to have completed study treatment if he/she has received a dose of mepolizumab at Visit 7 (Week 20) of the study. A participant is considered to have completed the study if he/she has completed the 24 week treatment period of the study including the end of study visit. The end of the study is defined as the date of the last visit of the last participant in the study.

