6.2. SAFETY POPULATION

All participants who take at least 1 dose of study intervention. This population will be used for all safety, efficacy and health outcomes.

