10. STATISTICAL ANALYSIS

All analyses of safety data and efficacy data will be generated for the Safety Population. All p values and 2-sided confidence intervals will be considered nominal without multiplicity control. Additionally, separate subgroup analyses will also be generated by with/without baseline maintenance OCS use (with separate summaries in those participants receiving maintenance OCS at baseline and those not maintenance OCS at baseline).

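### The SAP pools participants from the earlier mandated-taper design with Amendment 4 participants and never separates them, so the pooled and OCS=Yes results mix two background steroid regimens

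*SAP*

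**What the plan says.** Protocol 4.2 states that the OCS-sparing effect is "only to be assessed in patients who completed or withdrew from the study prior to the adoption of protocol amendment 4". This is current text, and it confirms that an earlier cohort exists. The protocol's summary of changes describes how that cohort was handled. It was one "where a structured OCS tapering schedule was mandated within the previous study protocols and protocol amendments", and it entered under a different steroid criterion: "Inclusion criteria 5 has been updated with respect to the removal of requirement for background systemic corticosteroids". The log is used here only as a fact about the earlier design.

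For the current design, SAP 5.1 says that "OCS use and OCS dose adjustment in participants will be as per the investigator's discretion and clinical practice".

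The SAP does not carry this distinction into the analysis:

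- SAP 4 gives every estimand the same treatment condition: "Treatment condition: Participants to receive Mepolizumab 100mg SC every 4 weeks during 24 weeks treatment period".
- SAP 6.2 defines the Safety Population as "All participants who take at least 1 dose of study intervention".
- SAP 10 says that "All analyses of safety data and efficacy data will be generated for the Safety Population", and then that "separate subgroup analyses will also be generated by with/without baseline maintenance OCS use". SAP 10.5 and 11 repeat baseline OCS (yes, no) as the only subgroup factor.
- The exacerbation model (SAP 10.2.1) has time period as its only covariate.
- The MMRMs (SAP 10.2.2 to 10.2.4) adjust for visit or reporting period, baseline maintenance OCS use and prior-year exacerbations.
- The table list in SAP Appendix 5 shows no display by protocol version for adverse events or any secondary endpoint.

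**The concern.** A mandated taper and discretionary OCS are different background treatments, and the documents show how the difference could reach the endpoints. Protocol 8.2.5 lists signs of adrenal insufficiency to be looked for on steroid withdrawal. If these are reported as adverse events, they enter the primary endpoint. Protocol 8.1.2 judges an exacerbation in a maintenance user against the existing maintenance dose, and a taper moves that reference during follow-up. Lung function, ACQ-5 and morning PEF may also respond to a change in background steroid.

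If so, the pooled estimate depends on how many people enrolled before Amendment 4. The one stratifier provided does not solve this, because it is tied to protocol version. Under the earlier entry criterion everyone should be OCS=Yes, so OCS=No should come entirely from Amendment 4. A reader who sees different results in the two displays could credit OCS status with what is really a difference in protocol version. The primary adverse event summaries and all seven secondary endpoints are exposed.

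**Working it through.** **The plan's own figures.** The concern disputes none of them, and they reproduce. P(at least one participant with an AE of true risk 2%, n = 100) = 1 − 0.98^100 = 0.8674, against 0.8673 in the table. Screening: 100 / (1 − 0.35) = 153.8, so 154.

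**Who falls in which stratum.** The inputs from the documents are a total of 100 (Protocol 9.2) and OCS=Yes for all earlier-design participants (inferred from the removed criterion). Two inputs are assumed because the documents do not give them: m, the number from the earlier design, taken as 10 to 75; and q, the share of Amendment 4 participants on OCS at baseline, taken as 0.1 to 0.5.

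- OCS=Yes count: y = m + q(100 − m)
- OCS=No count: n0 = (1 − q)(100 − m), with no earlier-design participants
- Earlier-design share of OCS=Yes: w = m / y
- Correlation of OCS status with version: phi = m·n0 / √[m(100 − m)·y·n0]

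Example with m = 25 and q = 0.3: y = 25 + 22.5 = 47.5; n0 = 52.5; w = 25/47.5 = 0.53; phi = 1312.5 / √(25 × 75 × 47.5 × 52.5) = 0.61.

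**How a version effect would look.** Assume, purely for illustration, exacerbation rate ratios of 0.6 under the earlier design and 0.4 under Amendment 4, equal pre-period rates, equal follow-up, and no true effect of OCS status. Then OCS=Yes shows 0.6w + 0.4(1 − w), OCS=No shows 0.40, and the pooled result is 0.6(m/100) + 0.4(1 − m/100).

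| m | q | OCS=Yes n | Earlier-design share | OCS=No n | phi | OCS=Yes ratio | Pooled ratio |
|---|---|---|---|---|---|---|---|
| 10 | 0.5 | 55 | 18% | 45 | 0.30 | 0.436 | 0.42 |
| 10 | 0.1 | 19 | 53% | 81 | 0.69 | 0.505 | 0.42 |
| 25 | 0.3 | 47.5 | 53% | 52.5 | 0.61 | 0.505 | 0.45 |
| 50 | 0.3 | 65 | 77% | 35 | 0.73 | 0.554 | 0.50 |
| 75 | 0.1 | 77.5 | 97% | 22.5 | 0.93 | 0.594 | 0.55 |

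Over the full grid the earlier-design share of OCS=Yes runs from 18% to 97%, and phi from 0.30 to 0.93. The apparent gap between strata runs from 0.436 − 0.40 = 0.04 to 0.594 − 0.40 = 0.19, with no OCS effect present.

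**What splitting by version costs.** The chance of seeing at least one participant with a 2%-risk AE is 1 − 0.98^n: 0.397 at n = 25, 0.636 at n = 50, 0.780 at n = 75 and 0.867 at n = 100. Version-specific safety displays can describe, but they will miss uncommon events.

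**The case against.** The best defence is that the plan already responds to the design change. The protocol's summary of changes records that Amendment 4 added OCS-stratified reporting and the OCS covariate, and the SAP carries both through. The exacerbation comparison is within-subject, before against after, and is repeated by OCS stratum. No hypothesis is tested, p-values are nominal and the safety results are descriptive. In the MMRM the reported quantity is the visit mean; the OCS coefficient is only an adjustment. Cohort sizes are unknown, and the earlier cohort could be small.

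Much of this stands, and it rules out several stronger readings that a reader might infer:

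- That both OCS subgroups mix regimens. OCS=No should be a single-design stratum.
- That the SAP plans an invalid OCS comparison. It plans separate summaries, so the confounding affects interpretation of the two displays, not a specified test.
- That the OCS stratifier and covariate should be replaced. Protocol 9.4 and 9.4.2 specify them, and dropping them would depart from the protocol.

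The defence does not show that OCS status can stand in for protocol version. Within OCS=Yes, taper and discretionary participants remain indistinguishable, and the exacerbation model has neither an OCS nor a version term. Prior-year exacerbations in the MMRM do not capture version either.

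**Conclusion.** The concern holds in a limited form. The pooled results and the OCS=Yes stratum combine two background steroid regimens, and no readable SAP text lets a reader separate them. Informal comparison of the OCS=Yes and OCS=No displays is confounded with protocol version. This is a worthwhile improvement, not a flaw that invalidates the planned analyses.

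The size is unknown. The documents give neither the number treated under each design nor any evidence that the taper changed an outcome in this study. A reader might take the 0.04 to 0.19 gap above as an estimate of bias. It is not; it follows entirely from assumed rate ratios and cohort shares. If few people enrolled earlier, the pooled effect will be small, but the planned outputs would not show that.

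The conclusion rests on two assumptions. First, the superseded criterion 5 made every earlier participant OCS=Yes; its full text is not available, only the description of its removal. Second, no version-based split sits in text not shown. The second matters most for the OCS-reduction tables (14.2.1.x). Their titles name the whole Safety Population although Protocol 4.2 limits the assessment to the earlier cohort. The exploratory endpoint sections are largely blank, so a restriction may exist there.

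**What to change.** Keep the pooled analyses, the OCS yes/no subgroups and the baseline OCS covariate as the protocol specifies. Then add the following:

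1. A derived protocol-version flag with three levels: completed or withdrew before Amendment 4 was adopted; ongoing at adoption; first dosed after adoption. A flag based only on the version in force at first dose would put the ongoing participants with those treated wholly under the earlier design, and would not match the cohort named in Protocol 4.2.
2. Descriptive displays of disposition, the primary adverse event summaries and the seven secondary endpoints by this flag, at least within OCS=Yes.
3. Sensitivity models: version as an added covariate in the MMRMs, and a period-by-version term in the exacerbation model where event counts allow. Hospitalisation and ED events may be too few.
4. Restriction of Tables 14.2.1.x to the cohort in Protocol 4.2, unless text not shown already does this.
5. A statement in the SAP and report that OCS yes/no displays are confounded with protocol version.

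The cost is one derived variable, some SAP wording and a few extra tables, with no new assessments of participants. With no hypothesis tests planned, the added displays raise no multiplicity issue. The drawback is small cells, so the displays by version should be read as descriptive.

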10.1. EFFICACY ANALYSIS SRATEGY

10.1.1. SECONDARY EFFICACY ENDPOINTS

There are no primary efficacy endpoints defined for this study. The efficacy analysis is defined in terms of secondary and other efficacy endpoints as below:

10.1.2. Secondary Endpoints:

- Number of clinically significant exacerbations.
- Number of exacerbations requiring hospitalization or ED visits
- Number of exacerbations requiring hospitalization
- Change from baseline in clinic pre-bronchodilator FEV1 at week 24
- Change from baseline in clinic post-bronchodilator FEV1 at week 24
- Change from baseline in ACQ-5 score at week 24
- Change from baseline in morning PEF during weeks 20 24.

10.1.2. Health Outcome Endpoints:

- Clinician and Subject rated response to therapy at Week 24
- Mean change from baseline in WPAI-GH composite scores (percentage) at week 24:
 - Percent work time missed due to general health
 - Percent impairment while working due to general health
 - Percent overall work impairment due to general health
 - Percent activity impairment due to general health

10.1.3. Exploratory Endpoints:

10.2. STATISTICAL METHODS FOR SECONDARY EFFIACACY ENDPOINTS

10.2.1. Asthma Exacerbations:

The number of clinically significant asthma exacerbations (including exacerbations requiring hospitalization or ED visits) that occur while on treatment will be analyzed using Negative Binomial regression using generalized linear model with a covariate of time period (pre-, post-mepolizumab as ordinal variable) with follow-up time within each period included as an offset within the model. The exacerbation rates during the pre- and post-treatment with mepolizumab will be presented, including comparison of pre- and post-mepolizumab exacerbation rates along with the with 95% confidence limits and corresponding p-value. Exacerbations separated by less than 7 days will be treated as a continuation of the same exacerbation. The following SAS code will be used:

where exbnum = number of clinically significant asthma exacerbations

period = pre- and post- mepolizumab treatment periods in which the exacerbation occurred logtime = \log_e (length of time in years in pre- mepolizumab and post- mepolizumab periods) Length of time (years) in study will be calculated as length of time (days)/365.25.

An unstructured covariance structure will be used in the model. If there are any convergence issue, then an alternative exchangeable or compound symmetric, autoregressive (AR (1)), Toeplitz covariance structure will be used. The variance of the mean estimate will be corrected for within-subject correlation by using REPEATED statement for subject in the GENMOD procedure.

The period of time for which exacerbation information will be included in the post-mepolizumab period will be from the start of treatment until the week 24 visit, regardless of treatment discontinuation. For

those participants with premature study withdrawal, the time period will include from the start of treatment until the date of withdrawal. Missing data (following early withdrawal) will be assumed to be missing at random (MAR) following subject withdrawal from the study.

In addition, a similar analysis will be conducted for frequency of exacerbations requiring hospitalization or ED visits and frequency of exacerbations requiring hospitalization if there are enough subjects in the corresponding category.

Treatment policy strategy will be used for intercurrent event treatment discontinuation (for any reason). This will estimate the treatment effect at the end of the 24 week study period regardless of treatment discontinuation.

Treatment policy strategy: The occurrence of the intercurrent event is considered irrelevant in defining the treatment effect of interest. The value for the variable of interest is used regardless of whether or not the intercurrent event occurs.

Counts and percentage of subjects with any exacerbations, any clinically significant exacerbations, any exacerbations requiring hospitalization or ED visit and any exacerbations requiring hospitalization during the treatment period will be provided for the safety population. The same output will also be presented regardless of treatment discontinuation. In such case even if a patient not received the treatment but passed the screening and discontinued are also counted for the variable of interest.

The rate of exacerbations requiring hospitalization or ER visit and rate of exacerbations requiring only hospitalization during the on-treatment period will be analysed using Negative Binomial regression model similar to the analysis for the rate of clinically significant exacerbations as described above. In addition, counts and percentage of subjects with the number of exacerbations (eg. 0, 1, 2, 3, 4, 5, 6, 7, 8, 9, >=10) during the on-treatment period will be presented.

10.2.2. Forced Expiratory Volume in 1 second (FEV1)

Analysis of change from baseline in clinic pre-bronchodilator FEV1 at Week 8, Week 16 and Week 24 will be performed using a mixed models repeated measures (MMRM) analysis, including visit and asthma exacerbations in the year prior to the study (as an ordinal variable -0, 1, 2, 3+) and baseline maintenance OCS use (yes, no) (binary nominal variable) as an as covariates. Change from baseline in pre-bronchodilator FEV1 value along with a two-sided 95% confidence interval and p-value estimated from MMRM model will be presented. The following SAS code will be used:

proc mixed data=modeldata; class usubjid avisitn; model chg = avisitn BASEOCSD PEXACCTN / solution ddfm=kr cl htype=**3**; Ismeans avisitn / cl pdiff e; repeated avisitn / subject= usubjid type=un; run;

Where, chg = change from baseline in clinic pre-bronchodilator FEV1 at Week 8, Week 16 and Week

Avisitn = Visit BASEOCSD = baseline maintenance OCS use (Yes/No) PEXACCTN = asthma exacerbations in the year prior to the study

An unstructured covariance structure will be used in the model. If there are any convergence issue, then an alternative compound symmetric, autoregressive (AR(1)), Toeplitz covariance structure will be used.

Treatment policy strategy will be used for treatment discontinuation (for any reason). This will estimate the treatment effect at the end of the 24 week study period regardless of treatment discontinuation.

Treatment policy strategy: The occurrence of the intercurrent event is considered irrelevant in defining the treatment effect of interest: the value for the variable of interest is used regardless of whether or not the intercurrent event occurs.

A similar analysis will be conducted for the post-bronchodilator FEV1 value at Week 24. In addition, descriptive summaries for the actual and change from baseline values for pre- and post-bronchodilator FEV1 will be presented by scheduled visits.

